Participants will be allowed to sleep as they are able immediately with the lights turned off at their habitual bedtime (bedtime is at hour 1, approximately 22:00-00:00). Nursing staff will use dim red lights (safelights) when collecting CSF and blood in the dark. The lumbar catheter ports will be placed on the outside of the gown sleeve for easy access to minimize disturbance during fluid collection. Participants will then sleep until final awakening in the morning. During Day 2, all participants will be in well-lit rooms with regular monitoring for staying awake and naps will not be permitted. At ~22:00 on Day 2 (hour 25), all participants will follow the same sleep routine except that there will be no infusion of labeled ¹³C₆-leucine. However, the time of hour 25 will depend on the participant's regular bedtime. Participants will receive the same placebo or lemborexant dose as the previous night (Fig 6). The study will end at ~20:00 on Day 3 (hour 48) when the IVs and lumbar catheters will be removed. All participants will then sleep overnight and will be monitored for at least 8 hours after catheter removal and then discharged. CSF tau, phosphorylated tau, and A_β kinetics will be quantified by mass spectrometry as was done for our previous work^{3,5}.

Table 2: Timeline of Catheter Placement and Removal, Bedtime, and Sampling														
Hour	0	1	2	4	6	8	10	12	14	16	18	20	22	24
Event	C, X	B	X	X	X	X	X	X	X	X	X	X	X	X
Hour	25	26	28	30	32	34	36	38	40	42	44	46	48	49
Event	B	X	X	X	X	X	X	X	X	X	X	X	X, R	B

C: catheter placement; B: bedtime; X: CSF/blood sampling; R: catheter removal

Table 3: Recruitment Using Plasma Aβ			
	Amyloid+	Amyloid-	Total
Tests positive	20	13	33
Tests negative	5	63	68
Total	25	76	101

positive on the plasma A β test are eligible for the study. The plasma A β test has an 80% sensitivity, 83% specificity for amyloid-positivity after accounting for age and ApoE genotype. Assuming that 25% of the cognitively normal population will be amyloid-positive, we plan to screen 100 cognitively normal participants with an PSQI>5 to obtain ~20 amyloid-positive cognitively normal individuals (Table 3). We expect to recruit the remaining participants from the Knight Alzheimer's Disease Research center (ADRC) and on-going studies at Washington University such as the SEABIRD study.

3.3 Power Calculation:

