All participants will take lemborexant on the Clinical Translational Research Unit at Washington University which has 24 hours a day nursing coverage monitoring the participants. Participants will only take lemborexant in this monitored setting. Nurses will be available to assist all participants if they develop these symptoms. Further, the participants will be under constant video monitoring while in the Clinical Translational Research Unit; this video is not recorded and is only viewable by the nursing staff. Lemborexant will be discontinued if reactions are distressing to the participant or severe. Participants will be monitored in the Clinical Translational Research Unit prior to discharge and will be assessed for level of alertness with a Stanford Sleepiness Scale and Psychomotor

Lemborexant 25 mg Overview

[name], Washington University

Vigilance Testing performed upon admission and at the time of discharge. The principal investigator will evaluate the participant and review these measures prior to approving discharge. Potential adverse events from lemborexant include:

- Somnolence: Somnolence may be severe in participants with compromised respiratory function; therefore, obstructive sleep apnea and chronic obstructive pulmonary disease are exclusion criteria. Lemborexant will be discontinued if somnolence is distressing to the participant or severe.
- Next day drowsiness
- Additional mild and common reactions to lemborexant include headache, and abnormal dreams
- Abnormal sleep behaviors
- Additional uncommon and rare reactions include heart palpitations, tachycardia, sleep paralysis, hypnagogic/hypnopompic hallucinations, and mild cataplexy-like symptoms.
- Lemborexant may interact with multiple medications: Participants taking medications that interact with lemborexant will be evaluated by the principal investigator. If the potentially interacting medications cannot be discontinued, then the participants will be excluded from the study.

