A clinical determination will be made, as to the likelihood that an AE is related to the administration of the study drug or research visit procedure. The PI or designee will determine the criteria below for the severity/intensity of the AE and its relationship to the administration of the investigational study drug. Other etiologies such as pre-existing conditions, concomitant therapy, study-related procedures, accidents that occur while on study, and other external factors will be considered during the evaluation of relatedness. The adverse event assessment report will be submitted with any reportable adverse event.

11.9 Severity/Intensity:

An adverse event will be classified as one of the following to describe the severity (intensity) and any necessary action taken in an attempt to resolve the event:

- Mild: A mild AE is usually transient in nature and generally does not interfere with normal activities. Participants are asymptomatic or have mild symptoms; intervention is not indicated.
- Moderate: A moderate AE is sufficiently discomforting to interfere with normal daily activities. Participants may need minimal, local, or noninvasive intervention;
- Severe: Also referred to as *medically significant* but not immediately life-threatening; hospitalization or prolongation of hospitalization is indicated; disabling; limiting self-care activities of daily living (ADL). Note that a severe event is not necessarily a serious event.
- Life Threatening: Any AE that places the participant, in the view of either the PI or designee, at immediate risk of death from the AE as it occurred. It does *not* include an AE that, had it occurred in a more severe form, might have caused death.

11.10 Attribution:

The degree of certainty about causality will be graded using the following relationship categories:

- Unrelated: An adverse event is *clearly not related* to the drug or procedure.
- Unlikely Related: An adverse event is *doubtfully related* to the drug procedure.
- Possibly Related: An adverse event is *may be related* to the drug or procedure.
- Probably Related: An adverse event is *likely related* to the drug or procedure.
- Definitely Related: An adverse event is *clearly related* to the drug or procedure.
- For the purposes of regulatory reporting, a causality assessment of unlikely related will be managed as “unrelated”. An adverse event that is definitely, probably, or possibly related will be managed as “related” and considered a “reasonable

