- *Adverse Event Reporting Period:* Serious adverse events and Adverse events, regardless of the causal assessment to the study interventions (lemborexant, lumbar catheter, etc.), are collected from the time the subject signs the study informed consent through 28 days after the participant's last dose of lemborexant. Serious adverse events will be reported directly to Eisai.
 - Expected adverse events (*i.e.*, are listed above and on consent forms) will be discussed at DSMC meetings. Also, they will be reported to the HRPO during annual renewals.
 - Unexpected serious adverse events will be reported within 10 days, per HRPO requirements.

Anticipated adverse events that would require medical intervention are:

- A post-lumbar catheter headache that does not resolve with conservative measures such as rest, hydration, and caffeine intake. This will be treated with “blood patch” in the Clinical Translational Research Unit, at no cost to the participant.
- Side effects to lemborexant such as somnolence and confusion upon waking. Risks from lemborexant are minimized with the inclusion/exclusion criteria and that participants will only receive the drug for 2 nights in the monitored setting of the Clinical Translational Research Unit at Washington University. If any severe adverse events occur after the first dose of lemborexant, then the drug will be discontinued and the participant monitored closely.

14. Potential Benefits of the Proposed Research to Human Subjects and Others

14.1 Potential benefits to participants:

The only direct benefit to the participant is that they will be screened for sleep apnea with the STOP-Bang questionnaire and other sleep disorders by the history and examination of the principal investigator. This may result in a diagnosis that may have otherwise been undetected. Participants who screen fail due to concerns for a sleep disorder like sleep apnea will be informed of the reason for exclusion, withdrawn from the study, and encouraged to follow-up with their primary care physician.

14.2 Potential benefits to others:

Potential benefits to society will be knowledge of whether or not sleep modification can change CSF A β production and concentrations. If CSF A β production and concentrations can be modified by improving sleep efficiency, then this opens up a new potential treatment option for the prevention or treatment of Alzheimer's disease from which they, or future AD patients, may benefit.

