18. APPENDICES

18.1 Appendix 1: Lemborexant 25 mg Safety Data

Introduction

Lemborexant (LEM) is a dual orexin receptor antagonist approved in the US, Japan, Canada, Australia, and other Asian countries for the treatment of adult patients with insomnia. Doses of 2.5 (LEM 2.5; Japan only), 5 mg (LEM5) and 10 mg (LEM10) are currently approved for these patients. Across the clinical program, a total of 150 subjects in 7 studies were exposed to lemborexant (E2006) 25 mg (LEM25). Multiple doses of LEM25 were evaluated in three multiple dose studies, E2006-A001-002, E2006-A001-003, and E2006-G000-201, which are described in more detail below. Other studies not included in this overview employed single dose paradigms.

Study E2006-A001-002 (NCT01673451)

Study Design

This was a single-center, randomized, double-blind, placebo-controlled, sequential, multiple-dose study. The study was conducted in 2 parts: Part A (6 cohorts of healthy adults receiving evening dosing) and Part B (1 cohort of elderly adults receiving evening dosing).

In Part A, it was planned for a total of 48 healthy adult subjects (18 to 55 years) to be enrolled into 1 of 6 cohorts sequentially in a gradual dose escalation manner, randomized to receive either LEM or matching placebo in the evening 30 minutes before habitual bedtime, and after 3 hours fasting, each night for 14 days. Each cohort was comprised of 6 LEM- and 2 placebo-treated subjects. Blood samples were collected for PK analysis at prespecified timepoints, and PD assessments were conducted (not reported here).

During Part B, one cohort of 8 elderly subjects (≥ 65 to 80 years) were randomized and treated for 14 days in the evening with LEM25 or matching placebo 30 minutes before habitual bedtime, and after 3 hours fasting. This cohort comprised 6 LEM- and 2 placebo-treated subjects. Blood samples were collected at prespecified timepoints, and PD assessments were conducted.

Overall, 55 subjects were randomized, and all received study drug (placebo, lemborexant 2.5 mg, 5 mg, 10 mg, 25 mg, 50 mg, 75 mg). A total of 11 subjects (6 adult, 5 elderly) were randomized to LEM25.

Summary of Adverse Events

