There appeared to be more treatment-related TEAEs with increasing doses of LEM, and the overall incidence of TEAEs was higher in LEM (all doses) (92.7%) compared to placebo (78.6%). There were no serious TEAEs. In the LEM groups, 1 subject (2.4%) in the LEM25 group had a TEAE leading to study drug dose adjustment and withdrawal from the study.

Lemborexant 25 mg Overview
[name], Washington University

This subject discontinued study drug due to an AE (pyrexia) that was not considered to be related to study drug and was withdrawn from the study (Table 1).

Table 1 Overview of Treatment-Emergent Adverse Events – Safety Analysis Set, Study E2006-A001-002

Category	Placebo (N=14)	E2006							E2006 Total (N=41)
		2.5mg (N=6)	5mg (N=6)	10mg (N=6)	25mg (N=6)	25mg Elderly (N=5)	50mg (N=6)	75mg (N=6)	
TEAEs	11 (78.6)	5 (83.3)	5 (83.3)	6 (100)	5 (83.3)	5 (100)	6 (100)	6 (100)	38 (92.7)
Treatment-related TEAEs^a	6 (42.9)	3 (50.0)	3 (50.0)	4 (66.7)	4 (66.7)	5 (100)	6 (100)	6 (100)	31 (75.6)
Severe TEAEs	0	0	0	0	0	0	0	0	0
Serious TEAEs	0	0	0	0	0	0	0	0	0
Deaths	0	0	0	0	0	0	0	0	0
Other SAEs	0	0	0	0	0	0	0	0	0
Life Threatening	0	0	0	0	0	0	0	0	0
Requires inpatient hospitalization or prolongation of existing hospitalization	0	0	0	0	0	0	0	0	0
Persistent or significant disability or incapacity	0	0	0	0	0	0	0	0	0
Congenital anomaly / birth defect	0	0	0	0	0	0	0	0	0
Important medical events	0	0	0	0	0	0	0	0	0
TEAEs leading to study drug dose adjustment	0	0	0	0	1 (16.7)	0	0	0	1 (2.4)
TEAEs leading to study treatment withdrawal	0	0	0	0	1 (16.7)	0	0	0	1 (2.4)

Table 1 Overview of Treatment-Emergent Adverse Events – Safety Analysis Set, Study E2006-A001-002

Category	Placebo (N=14)	E2006							E2006 Total (N=41)
		2.5mg (N=6)	5mg (N=6)	10mg (N=6)	25mg (N=6)	25mg Elderly (N=5)	50mg (N=6)	75mg (N=6)	

Placebo group includes placebo subjects pooled from all cohorts in the study. Percentages are based on the total number of subjects in relevant treatment group.

For each row category, a subject with 2 or more adverse events in that category is counted only once. MedDRA = Medical Dictionary for Regulatory Activities; TEAE = treatment-emergent adverse event, SAE = serious adverse event.

a: Includes TEAEs considered by the investigator to be possibly or probably related to study drug or TEAEs with missing causality. MedDRA Version 16.0.

Source: [Table 14.3.1.2](#).

Serious Adverse Events – Safety Analysis Set

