No TEAEs in any treatment group were severe. The adult LEM groups that reported only mild TEAEs were 2.5, 5, 10, and 25 mg. In the elderly LEM25 group, there was one TEAE of somnolence and one TEAE of hypoxia, both of which were rated moderate.

Overall Safety Conclusions

LEM was safe and well-tolerated following dosing in adult subjects up to 75 mg per day for 14 days, and in elderly subjects receiving 25 mg per day for 14 days. There was a higher incidence of treatment-related TEAEs among LEM subjects (all doses) (31/41, 75.6%) compared to placebo subjects (6/14, 42.9%). The incidence of treatment-related TEAEs appeared to be dose-related with higher rates occurring at higher doses, the highest incidence (100%) occurring in the LEM25 elderly, LEM50, and LEM75 dose groups. However, most TEAEs were mild in severity. No SAEs were reported during the study.

Study E2006-A001-003 (NCT02039089)

Study Design

This was a single-center, multiple-dose, randomized, double-blind, placebo-controlled, parallel-group study in healthy male and female subjects. The study consisted of 2 parts: Part A (3 cohorts of healthy Japanese subjects dosed in the evening) and Part B (1 cohort of healthy white subjects dosed in the evening). The cohorts were conducted sequentially. Part A was started first with the 2.5-mg dose cohort, followed by the 10-mg dose cohort, and then the 25-mg dose cohort. Part B was conducted in parallel with the 10-mg cohort of Part A, with overlap. Subjects received treatment with study drug for 14 days.

Summary of Adverse Events

The number of subjects with TEAEs and the incidence of TEAEs were low and similar across dose groups. No trends with dose or race were seen. Most TEAEs were judged by the investigator to be treatment related (i.e., related or not related as described in the clinical study protocol to study drug). All TEAEs were mild. There were no severe TEAEs, serious TEAEs, TEAEs leading to withdrawal, or deaths during the study. All TEAEs resolved by the end of the study.

Somnolence and abnormal dreams were the most frequently reported treatment-related TEAEs, with 4 Japanese subjects (1 each in the placebo and 2.5-mg groups, and 2 in the 25-mg group) and 1 white subject (10-mg group) reporting somnolence and 1 Japanese subject (25-mg group) and 2 white subjects (10-mg group) reporting abnormal dreams (Table 2).

Table 2 Summary of Treatment-emergent Adverse Events (Safety Analysis Set, Study E2006-A001-003)

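### Withholding the second dose is required only after a distressing or severe reaction, so a moderate or unfelt night-1 hypoxia event is left to judgement; and the respiratory exclusions cited in section 10.5 do not match section 7.3.2

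*Combined protocol and SAP*

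**What the plan says.** Two places oblige staff to stop the drug for an individual. Section 10.5 states: "Lemborexant will be discontinued if reactions are distressing to the participant or severe". Section 13.2 states: "If any severe adverse events occur after the first dose of lemborexant, then the drug will be discontinued and the participant monitored closely". Otherwise section 3.1 repeats the same treatment on the second night, at hour 25.

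Section 11.9 defines the grades. For mild it says: "Participants are asymptomatic or have mild symptoms; intervention is not indicated". Moderate means discomfort that interferes with daily activities, possibly with minimal, local or noninvasive intervention. Severe is also called medically significant, and is described by hospitalization, disability or limits on self-care. No grade carries a saturation or other respiratory value.

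Appendix 1 (Study E2006-A001-002) includes elderly subjects aged 65 to 80 "treated for 14 days in the evening with LEM25 or matching placebo". It reports: "In the elderly LEM25 group, there was one TEAE of somnolence and one TEAE of hypoxia, both of which were rated moderate". Of the adult cohorts it says: "The adult LEM groups that reported only mild TEAEs were 2.5, 5, 10, and 25 mg". In its Table 1, the row "TEAEs leading to study drug dose adjustment" shows 0 for the elderly 25 mg column (N=5).

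On entry, section 10.5 treats obstructive sleep apnea (OSA) and COPD as exclusion criteria, because somnolence may be severe when respiratory function is compromised. Section 7.3.2 admits mild apnea (AHI below 16) and leaves pulmonary disease to PI discretion. Section 3.1 says only moderate or severe OSA excludes.

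**The concern.** Participants aged 60 to 80, some with mild apnea, take 25 mg on two consecutive nights. That is 25/10 = 2.5 times the highest approved dose. The sponsor's own appendix records a moderate hypoxia event at this dose in this age range, and moderate is a grade at which the dosing rule obliges nobody to act unless the participant was distressed. Distress is also a weak trigger for someone asleep after taking a hypnotic.

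The plan could thus be followed exactly and a participant with a moderate or unfelt hypoxia event on night 1 could receive the same treatment 24 hours later. The investigator may withhold it, but the text does not require that, and it does not say that night-1 events are reviewed before hour 25. The entry protection that 10.5 leans on is also narrower in 7.3.2 than 10.5 states.

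**Working it through.** **1. What the rules require after night 1**

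| Night-1 hypoxia event | Likely grade under 11.9 | Dose 2 must be withheld? |
|---|---|---|
| Unfelt, no intervention | Mild | No |
| Managed noninvasively, not distressing | Moderate | No |
| Any grade, distressing to the participant | Any | Yes (10.5) |
| Judged medically significant, or hospitalization indicated | Severe | Yes (10.5, 13.2) |

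The first two rows are the gap. The last row is wider than it looks, because an investigator may use the medically significant wording for an important desaturation.

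**2. Whether saturation is recorded**

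The text available for this review does not name oxygen saturation or oximetry. Sections 7.4.4 and 8.1.3 list EEG, EOG and EMG. Section 8.2.11 lists blood pressure, pulse, temperature and respiration. None of these lists settles the matter: 7.4.4 gives the channels for sleep staging, 8.1.3 is worded as a partial list, and 8.2.11 describes the examination. Section 3.1 calls the inpatient recording full-montage, and Appendix 2 schedules vital signs during sampling without itemising them.

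**3. Size**

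The plan gives no figure to reproduce. Inputs are 1 hypoxia event, 5 elderly subjects and 14 nights (Appendix 1), and 20 participants on lemborexant (section 3.3). I assume a constant nightly rate and full dosing.

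- Elderly cohort alone: 5 × 14 = 70 person-nights. Rate 1/70 = 1.4% per night (exact 95% CI 0.04% to 7.7%). Expected night-1 cases 20/70 = 0.29 (CI 0.007 to 1.5). Chance of at least one: 1 − (69/70)^20 = 25%.
- Elderly cohort plus the 49-person respiratory study, assuming one 25 mg night each and no hypoxia there: 70 + 49 = 119 nights. Expected 20/119 = 0.17. Chance 1 − (118/119)^20 = 16%.
- All 25 mg exposure in Table 4 of Appendix 1, assuming no other case and one 25 mg night per person in the single-dose studies: 11×14 + 6×14 + 50×15 + (18+16+49)×1 = 154 + 84 + 750 + 83 = 1,071 nights. Expected 20/1,071 = 0.02. Chance 1 − (1,070/1,071)^20 = 2%.

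One event in 5 people is 20% per person, but over 14 nights, so it should not be applied to a single night. These figures count any hypoxia event, not only those that escape the rule, and they say nothing about unfelt desaturation that was never recorded.

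**4. What a withheld dose 2 would cost the analysis**

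CSF is sampled every 2 hours from 0 to 48, which is 25 samples: 13 up to hour 24 and 12 after hour 25. With the transit time of about 5 hours in section 1.4, dose 2 can show from hour 25 + 5 = 30, so hours 30 to 48 (10 samples) could reflect it. The windows used for power in section 3.3 are hours 14–18 for pT181/T181 and 22–26 for Aβ42, both before hour 30. The hour-36 pS202/S202 window and the later part of the longitudinal model in section 3.5 would be affected.

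**The case against.** The strongest case is that one event in five people, with its night, relatedness and symptoms not given, is thin evidence. Appendix 1 concludes that 25 mg for 14 days was safe and well tolerated in the elderly. It reports nothing new on safety at this dose in further studies, among them a placebo-controlled crossover study of respiratory safety in adults and elderly subjects, with 49 exposed to 25 mg. No elderly subject in Study E2006-A001-002 needed a dose adjustment or withdrawal. A reader might infer from the adult and elderly cohorts that age raises the risk at 25 mg. The documents do not support this: moderate hypoxia was 0 of 6 against 1 of 5, and a single event among 11 people falls in the elderly group by chance with probability 5/11 = 0.45.

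The safeguards are also real. Dose 1 is followed by half-hourly blood draws until hour 4, and nursing and video watch are continuous. Staff report adverse events at once to the PI, the team reviews data as they arrive, and physicians can be reached at any time. An unexpected serious event stops the trial, and the DSMC can suspend research. Moderate discomfort may also overlap with distress under 10.5.

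All of this stands, and it lowers the weight of the point. It does not supply a required action: none of these safeguards is tied to a respiratory finding or to the hour-25 dose. The half-hourly draws are not repeated on night 2, when scheduled draws fall at hour 26 and every 2 hours after.

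**Conclusion.** The gap in the rule is real and narrow. A moderate or unfelt night-1 hypoxia event leaves dose 2 to investigator judgement, and the exclusions cited in 10.5 do not match 7.3.2. On apnea the mismatch is mostly wording, since section 3.1 already limits the exclusion to moderate or severe OSA. On COPD it is substantive, because 7.3.2 would let the PI admit someone whom 10.5 says is excluded.

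The expected number of night-1 cases is small, 0.02 to 0.29 among 20 treated, and rests on a single event and a constant nightly rate. The low end further assumes no hypoxia in studies whose counts I could not see; the adverse-event results of Study E2006-G000-201 are among the text not available.

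Two stronger readings are tempting. One is that the trial does not measure oxygen saturation; the text leaves that open. The other is that 25 mg has a demonstrated respiratory hazard in older people; the respiratory safety study and the absence of new signals argue against it. I rate this a minor to moderate safety improvement.

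**What to change.** 1. In 10.5 and 13.2, with a cross-reference from 3.1, require that dose 2 of study drug be withheld in either arm after any night-1 hypoxia event graded moderate or worse, or needing supplemental oxygen. Have a study physician review night-1 events before hour 25. Writing the rule for study drug means nobody needs the allocation to apply it.
2. Confirm that the inpatient PSG or vital signs record pulse oximetry, or add bedside oximetry on both dosing nights, and show it in Appendix 2. Any saturation limit is for the sponsor to set; the documents give no basis for a value. Without one, an unfelt and untreated desaturation stays with the physician's review.
3. List COPD as an explicit exclusion in 7.3.2, and reword 10.5 to say that moderate or severe OSA is excluded. Relaxing 10.5 on COPD to PI discretion would also remove the mismatch, but it would weaken protection.
4. State that participants whose dose 2 is withheld continue CSF sampling and are analysed as randomised.

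The cost is some wording, one physician review per participant and, if not already in place, oximetry for two nights. Drug-related hypoxia would cost about 0.02 to 0.3 second doses among 20. If a saturation limit is added, background desaturation from admitted mild apnea could add 0 to 3 among all 30 participants, on an assumed rate of 0 to 10%. The loss is confined to samples after hour 25 and leaves the hours 14–18 pT181/T181 window untouched.
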